5.3.3.1. T1 Gd+ lesions

For summaries of total number of T1 Gd+ lesions (T1Gd_R) and T1 Gd+ lesion volume (T1Gd_Vol) over time, MRI scans are remapped to the nearest timepoint via a windowing approach. If a subject has more than one assessment within a given window, the nearest

```
CONFIDENTIAL – FOIA Exemptions Apply in U.S.
```

Status: Approved, Date: 20 September 2023

assessments to the (target) MRI timepoint within the window is taken. Only scheduled scans are remapped.

Time windows are derived from time since first administration of ponesimod according to the schedule defined in Table 8 below.

*	
Target timepoint displayed	Time window (weeks)
Baseline	Last non-missing prior or on day of 1 st ponesimod dose
Week 24	1 (Day 2) - < 32
Week 48	32 - < 60
Week 72	60 - < 96
Week 120	96 - < 144
Week 168	144 - < 192
Week 216	192 - < 240
Week 264	240 - < 288
Week 312	288 - < 336
Week 360	336 - < 384
Week 408	384 - < 432
Week 456	432 - < 480
Week 504	480 - < 528
Week 552	528 - < 576
Week 600	576 - < 624
Week 648	624 - < 672
Week 696	672 - < 720

 Table 8:
 MRI timepoint definition: scan mapping

The following variables are derived for T1 Gd+ lesions per subject:

- Total number of T1 Gd+ lesions (T1Gd_R) per MRI timepoint (as defined in Table 8 above) in AP3, and corresponding number categorized (0, 1, 2, 3, 4+);
- Cumulative total number of T1 Gd+ lesions over the Analysis Period, for AP3, defined as the sum of the total number of T1 Gd+ lesions at each derived MRI (mapped) timepoint;
- Number of derived MRI (mapped) timepoints in the Analysis Period, for AP3;
- Absence of T1 Gd+ lesions (lesion-free) per MRI timepoint in AP3 (only mapped scans are considered);
- Total volume of T1 Gd+ lesions per MRI timepoint in AP3.

5.3.3.2. New or enlarging T2 lesions and T2 volume

For summaries of new or enlarging T2 lesions (T2New_R) over time, the number of lesions is assigned to the timepoint in which they fall, as defined in Table 9 below. As the number of new or enlarging lesions is always relative to the previous assessment, if the observation period for the scan crosses the boundary of a time window, the lesions are allotted **proportionally** to the time windows which they cross. For example, if a subject has a scan at Week 24, and the next scheduled scan occurs at Week 72, the Week 72 scan will count the number ("x") of new or enlarging T2 lesions since Week 24. In this case x/2 lesions would be allocated to the Week 0-48 window, and x/2 lesions would be allocated to the Week 48-96 window.

Time windows are derived from time since first administration of ponesimod according to the schedule defined in Table 9 below.

Time window displayed	Time window (weeks)
Week 0-48	0 - <48
Week 48-96	48 - <96
Week 96-144	96 - <144
Week 144-192	144 - <192
Week 192-240	192 - <240
Week 240-288	240 - <288
Week 288-336	288 - <336
Week 336-384	336 - <384
Week 384-432	384 - <432
Week 432-480	432 - <480
Week 480-528	480 - < 528
Week 528-576	528 - < 576
Week 576-624	576 - < 624
Week 624-672	624 - < 672
Week 672-720	672 - < 720

Table 9:	MRI time window	definition: scan	mapping for new o	r enlarging T2 lesions
----------	-----------------	------------------	-------------------	------------------------

The following variables are derived for T2 lesions per subject using the above time windows:

- Number of new or enlarging T2 lesions (T2New_R) per MRI time window (as derived in Table 9 above) in AP3;
- No new or enlarging T2 lesions during each MRI time window in AP3.

The following additional variables are derived for T2 lesions per subject: Only scheduled scans are considered, however premature EOT scans are included.

- Cumulative number of new or enlarging T2 lesions over Analysis Period (for AP3), derived as the sum of the number of new or enlarging T2 lesions at each scheduled scan during the Analysis Period;
- Absence of new or enlarging T2 lesions over the Analysis Period (for AP3), derived where the sum of the number of new or enlarging T2 lesions at each scheduled scan during the Analysis Period is zero;
- Time (years) from first administration of ponesimod to last MRI scan at which T2 was measured in the Analysis Period (for AP3). Only scheduled scans are used for this derivation.
- T2 volume (T2_Vol) per MRI timepoint (as defined in Table 9 above) in AP3;
- Change from ponesimod baseline in total T2 lesion volume per MRI timepoint (as defined in Table 9 above) in AP3.

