5.3.4.2. New or enlarging T2 lesions

The cumulative number of new or enlarging T2 lesions (as defined in Section 5.3.3.2) is analyzed separately for AP3 on the PAS, as described in Section 5.3.4.1 for the cumulative total number of T1 Gd+ lesions. The logarithm of the time up to the last MRI scan at which T2 was measured in the Analysis Period (years) is used as an offset variable. This analysis was conducted for the Interim CSR and is not planned to be conducted for the Final CSR.

The number of new or enlarging T2 lesions per MRI time window (as defined in Section 5.3.3.2) is summarized descriptively by treatment group as described in Section 5.3.4.1 for the cumulative number of T1 Gd+ lesions, and is presented in both a table and a figure for AP3 on the PAS.

The total T2 lesion volume per MRI timepoint and corresponding change from ponesimod baseline in total T2 lesion volume per MRI timepoint are summarized descriptively in the same way.

The number of subjects with no new or enlarging T2 lesions (lesion-free) in the Analysis Period is summarized by treatment group separately for AP3 on the PAS: frequency counts and percentages. The denominator for percentages is the number of subjects with at least one MRI scan at which T2 was measured during the Analysis Period.

All T2 lesion and volume data are presented in a listing for AP3 on the PAS.

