5.3.4.3. CUAL

The cumulative number of CUAL (as defined in Section 5.3.3.3) is analyzed for AP3 on the PAS, as described in Section 5.3.4.1 for the cumulative total number of T1 Gd+ lesions. The logarithm of the time up to the last MRI scan at which T2 was measured in the Analysis Period (years) is used as an offset variable.

The number of CUAL per MRI time window (as defined in Section 5.3.3.2) is summarized descriptively by treatment group, as described in Section 5.3.4.2 for the cumulative number of new or enlarging T2 lesions, and is presented in both a table and a figure for AP3 on the PAS.

Frequency counts and percentages for the categorical number of CUAL in the Analysis Period are presented by treatment group for AP3 on the PAS. The denominator for percentages is the number of subjects with at least one MRI scan at which T2 was measured during the Analysis Period.

All CUAL data is presented in a listing for AP3 on the PAS.

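### Mean new or enlarging T2 counts per 48-week window ignore how much of the window was observed, so the last windows show a false fall

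*SAP*

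**What the plan says.** SAP 5.3.3.2 counts each scan's new or enlarging T2 lesions relative to the previous scan and assigns them to fixed 48-week windows from the first ponesimod dose. It divides them between windows in proportion to time "if the observation period for the scan crosses the boundary of a time window". Its worked example has scans at Weeks 24 and 72 with x lesions on the second: "In this case x/2 lesions would be allocated to the Week 0-48 window", and the other half goes to Week 48-96.

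The derived variable is a plain count: "Number of new or enlarging T2 lesions (T2New_R) per MRI time window (as derived in Table 9 above) in AP3". A yes/no variable is derived beside it: "No new or enlarging T2 lesions during each MRI time window in AP3".

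SAP 5.3.4.2 presents the count in a table and a figure. It "is summarized descriptively by treatment group as described in Section 5.3.4.1 for the cumulative number of T1 Gd+ lesions". SAP 5.3.4.3 does the same for combined lesions: "The number of CUAL per MRI time window (as defined in Section 5.3.3.2) is summarized descriptively by treatment group".

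Neither document gives the weeks of a window that a subject covered, a minimum coverage, a scaling to 48 weeks, or a denominator for these per-window summaries.

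**The concern.** The numerator is split by time, but the matching time at risk is not tracked. A subject whose last scan falls early in a window contributes a few weeks of lesions, and that value is averaged with full 48-week values. Follow-up ends in every subject, so the shortfall concentrates in the last windows and looks like falling MRI activity.

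The SAP handles the same problem elsewhere. For relapse rate by year, SAP 5.3.1.1 notes that a subject with 900 days has only 170 days in year 3, and the model in SAP 5.3.2.1 has a log-time offset. The cumulative CUAL model in SAP 5.3.4.3 has one too. The cross-reference to SAP 5.3.4.1 supplies nothing: the cumulative T1 model there is not planned for the final report, and its descriptive summaries have no time adjustment.

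The offset-adjusted cumulative T2 model is also dropped from the final report (SAP 5.3.4.2). The unadjusted per-window table and figure are then the remaining planned summary of T2 counts over time.

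**Working it through.** **1. The SAP's own example.** Share of a window = overlap of the scan interval with the window / length of the interval. Week 0-48: (48 - 24)/(72 - 24) = 0.5. Week 48-96: (72 - 48)/(72 - 24) = 0.5. Both halves reproduce. If Week 72 is that subject's last scan and the true rate is 1 per 48 weeks, Week 48-96 shows 24/48 = 0.5.

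**2. When scanning ends.** Inputs from the protocol: 24 weeks in the core study; P1 12 weeks after E9, E10, E11 or E12, which is extension Week 60, 72, 84 or 96 (3.1.1); 540 weeks of periods 2 and 3; yearly MRI plus EOT3 and a follow-up scan at FU2 (3.11.1.1), 30 days or 4.3 weeks after the last dose.

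- Ponesimod in the core study: 24 + (60, 72, 84, 96) + 540 = 624, 636, 648, 660 weeks. The last agrees with the 660-week maximum in Protocol 1.4.6.
- Placebo in the core study, counted from the first ponesimod dose: 600, 612, 624, 636 weeks.
- Latest scan with FU2: 660 + 4.3 = 664.3 weeks, which covers (664.3 - 624)/48 = 84% of Week 624-672.

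On these paths nobody covers Week 624-672 in full. Entry after E13 with a gap of about 13 weeks can reach about 677 weeks, at most 11% of Week 672-720.

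**3. Raw mean / true mean, no dropout.** Under a constant rate, expected count = rate x covered weeks, so the ratio is mean coverage whatever the rate. Assumed: 75% ponesimod and 25% placebo in the core study (1:1:1:1 randomization), the four entry times equally likely, and averaging over subjects with any coverage. Each ponesimod path has weight 0.1875 and each placebo path 0.0625.

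- Week 624-672, without FU2: [0.1875 x (0.25 + 0.50 + 0.75) + 0.0625 x 0.25] / 0.625 = 0.297/0.625 = 0.47.
- Week 624-672, with FU2: [0.1875 x (4.3 + 16.3 + 28.3 + 40.3) + 0.0625 x (4.3 + 16.3)] / 0.875 = 20.6 weeks; 20.6/48 = 0.43.
- Week 576-624, without FU2: 1 - 0.0625 x (0.50 + 0.25) = 0.95. With FU2 it is 0.96.

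**4. With dropout.** Simulation of 20,000 subjects on the same schedule, with an end-of-treatment scan at dropout. Ranges are with and without FU2.

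| Assumed dropout per year | Windows to Week 576 | Week 576-624 | Week 624-672 |
|---|---|---|---|
| 0% | 1.00 | 0.95-0.96 | 0.43-0.47 |
| 5% | 0.98 | 0.93-0.94 | 0.42-0.47 |
| 10% | 0.95-0.96 | 0.91-0.92 | 0.41-0.47 |

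Further runs on this schedule gave 0.42-0.44 in Week 624-672, 0.90-0.97 in Week 576-624 and mostly 0.92-1.0 earlier. Dividing by covered time gave a flat rate in every window of the tabulated runs, and was within about 6% of the true rate in the further runs.

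**5. CUAL.** Suppose Gd+ lesions are a share g of CUAL and enter as a whole count per scan. With 0.43 for the T2 part, Week 624-672 is 0.43(1 - g) + g x (scans in the window). One scan: 0.49 at g = 0.1 and 0.60 at g = 0.3. Two scans (EOT3 and FU2): 0.59 and 0.90. With two scans it passes 1 when 0.43 + 1.57g > 1, so g above about 0.36. The values of g are assumptions.

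**The case against.** The strongest reply is that the material effect sits in essentially one window. Pro rata allocation bridges missed scans, so a window between scans is fully covered and only each subject's final window is short. The retained MRI model, cumulative CUAL, carries a time offset. T1 Gd+ counts, T2 volume and brain volume are not affected. All objectives are exploratory (SAP 2), and the same rule applies to all three dose groups. The defect is also an omission: table shells, which are not available here, might supply a coverage rule. All of this stands, and it limits the importance of the point. It does not remove the late fall in T2, because the SAP as written contains no such rule.

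A reader might infer three stronger things that the documents do not support.

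- **Lesion-free status by window is biased toward lesion-free.** One lesion in an interval that crosses a boundary puts a fraction in both windows, so neither counts as lesion-free. In simulation (true rate 1.0 per 48 weeks, protocol schedule), about 0.19-0.30 were lesion-free in windows from Week 48 to 624, against a true 0.37. Only Week 624-672 was too high (0.58, with 5% yearly dropout). Coverage scaling does not correct the fractions. SAP 5.3.4.2 also plans a lesion-free summary only over the whole analysis period.
- **The bias always favours the drug.** The lesion-free result runs the other way in most windows, the net CUAL effect is undetermined, and the extension has no placebo or active comparator.
- **The last two windows lose about 18% and 83%.** Those figures require all scanning to end at Weeks 600-640, whereas Protocol 1.4.6 allows up to 660 weeks on ponesimod.

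**Conclusion.** The point holds for mean new or enlarging T2 counts. As written, the SAP produces a false late fall: about 40-47% of the true value in Week 624-672, about 90-97% in Week 576-624 and roughly 92-100% before that. The direction follows from the allocation rule and the missing covered time. The size rests on a constant lesion rate, dropout of 0-10% per year, an equal mix of entry times, and averaging over subjects with any coverage. Early exits, such as a switch to commercial ponesimod, would spread the shortfall to earlier windows.

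For CUAL per window, the T2 part is undercounted in the same way. The net effect is uncertain: SAP 5.3.3.3 attributes fractional values to T2 allocation only, does not say how Gd+ counts are placed in windows, and excludes only core Weeks 4, 8, 16 and 20 to avoid double counting. EOT3 and FU2 scans about 30 days apart could therefore both add Gd+ lesions.

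**What to change.** In SAP 5.3.3.2, derive the weeks of each window covered by scan intervals for every subject. In SAP 5.3.4.2 and 5.3.4.3, replace the mean count per window with the sum of allotted lesions divided by the sum of covered time, per 48 weeks or per year, for T2 and for the T2 part of CUAL. Show the number of subjects and the covered time beside each window. In SAP 5.3.3.3, state how Gd+ counts enter windows, including when EOT3 and FU2 scans fall close together.

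The cost is one derived variable, a few lines of SAP text and slightly wider late-window estimates. No new data are needed.

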The primary investigator / treating neurologist or the study nurse must instruct/remind the patient to interrupt the contraception until after delivery and to follow all the visits scheduled as per protocol during the study drug interruption period and until the study drug has been re-initiated or permanently discontinued.

3.12.5.5 Additional unscheduled visit for eligibility assessment for re-initiation of study drug for female subjects who interrupted the study drug for planned pregnancy and who wish to re-initiate the study drug after delivery

As described in Appendix 1 section D, female patients who interrupted the study drug for planned pregnancy and who wish to re-initiate the study drug after delivery will need to be assessed for eligibility for study drug re-initiation. Unless the patient has been treated with a disease modifying therapy (DMT; IFN β -1a or glatiramer acetate) during the pregnancy and post-partum, this visit should take place as soon as possible after delivery in order to minimize the post-partum period without MS treatment. In addition, this visit should take place 30 (±5) days before the study drug re-initiation.

Ponesimod / ACT-128800 / JNJ-67896153 Multiple Sclerosis Protocol AC-058B202 Version 12 15 March 2022, page 111/179

Confidential

EudraCT 2009-011470-15 EDMS-ERI-206617631

During this visit, the following assessments must be performed before study drug administration:

Urine pregnancy test first and, if urine pregnancy test is negative:

- PFTs (FEV₁ and FVC);
- Laboratory tests (central laboratory) preferably under fasting conditions: Hematology, blood chemistry, urinalysis;
- Assessment of methods of contraception;
- Recording of changes in concomitant medication, if any;
- Body temperature;
- Body weight;
- Physical examination;
- 12-lead ECG and SBP/DBP (under the responsibility of the physician evaluating cardiac safety assessments or primary investigator / treating neurologist);
- EDSS and FS assessment (performed by the evaluating neurologist);
- MRI examination;
- Ophthalmological examination (best corrected visual acuity, low contrast visual acuity testing, visual fields, and dilated ophthalmoscopy; OCT in case of suspected clinically significant findings [e.g., macular edema]);
- Recording of AEs and SAEs;
- Remind the patient to use the methods of contraception defined for this study. The reminders must be documented in the hospital chart;

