• The need to follow the visit schedule as per protocol during pregnancy including all the scheduled assessments and procedures except MRI, PFTs and without study drug dispensing.

The re-initiation of study drug after delivery requires the following eligibility criteria:

- The patient has completely stopped breastfeeding prior to re-initiation of the study drug;
- The patient must have been using the reliable methods of contraception as described in Section 4.4 for at least 30 days prior to re-initiation of study drug;
- The patient must have had 2 negative urine pregnancy tests performed 30 days apart; the second one must be during the re-initiation visit;
- The patient did/does not fulfill any protocol criteria for permanent study treatment discontinuation per Appendix 1 at any of the previous visits or at the unscheduled visit for re-initiation of the study drug except the planned pregnancy;
- In case the patient received another DMT (IFN β -1a or glatiramer acetate) during pregnancy and post-partum, this treatment must be discontinued at least 7 days before study drug re-initiation.

If the patient agrees to all of the above, the study drug will be interrupted at the scheduled visit once the patient, after having received the above explanation from the primary investigator / treating neurologist, has confirmed the wish to become pregnant and interrupt and potentially re-initiate the study drug. The sponsor has to be contacted in each particular case to confirm that the patient who wishes to become pregnant can continue in the study.

The above requirements for re-initiation of study drug after delivery apply to all cases of study drug interruption for planned pregnancy, irrespective of the duration of pregnancy and also to all cases where planned pregnancy did not occur but where the contraception was interrupted for any duration and the patient wishes to re-initiate the study drug.

E) Ocular abnormalities

In the event of suspected clinically significant findings (e.g., macular edema), an unscheduled ophthalmological assessment with OCT should be performed. In case of macular edema confirmed by the local ophthalmologist, the subject must permanently discontinue study treatment. Macular edema is to be managed and followed up until resolution. Any clinically relevant finding meeting the definition of an AE will be recorded accordingly in the eCRF.

Ponesimod / ACT-128800 / JNJ-67896153		EudraCT 2009-011470-15
Multiple Sclerosis		EDMS-ERI-206617631

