5.1.3. Planned Pregnancy Interruptions

Planned pregnancy interruptions will be excluded for definition of exposure, treatment-emergent adverse events and other safety variables including AEs, laboratory tests, pulmonary function tests (PFTs), vital signs and ECGs.

Planned pregnancy interruptions will not be excluded for efficacy analyses or for study duration.

Interruptions for planned pregnancies are identified in the database as defined in Section 5.2.1.5. Determination of the period of planned pregnancy interruption is described in Section 5.1.4.

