5.3.3.3. Combined unique active lesions (CUAL)

The following variables are derived per subject for CUAL:

- Total number of CUAL derived as the number of new or enlarging T2 lesions at each scheduled scan* within the Analysis Period, plus the number of T1 Gd + lesions at each corresponding scheduled scan within the Analysis Period where new or enlarging T2 lesions were measured (AP3), and corresponding number categorized (0, >0** 5, >5 10, >10 15, >15 20, >20 25, >25)
- Cumulative number of CUAL over the Analysis Period, derived as the sum of all new or enlarging T2 lesions at each scheduled scan* within the Analysis Period, plus the number of T1 Gd + lesions at each corresponding scheduled scan within the Analysis Period where new or enlarging T2 lesions were measured (AP3);
- Cumulative number of CUAL over the Analysis Period as derived above, categorized into the following categories: 0, 1-5, 6-10, 11-15, 16-20, 21-25, 26-30, 31-35, 36-40 and 41+ (AP3).

* Excluding T1 Gd+ lesions measured at the core scheduled visits at Week 4, 8, 16 and 20. This restriction is necessary to avoid double-counting lesions when the MRI scans are less than 12 weeks apart, as only total (new + persisting) T1 Gd+ lesions are collected, but the derivation of CUAL should consider only new T1 Gd+ lesions. As T1 Gd+ lesions are assumed not to enhance for more than 12 weeks, it is assumed that the number of T1 Gd+ lesions counted when the scans are at least 12 weeks apart is equivalent to the number of new T1 Gd+ lesions.

** Fractional values are possible and reflect allocation of T2 lesions proportionally to adjacent time-windows.

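### T2 lesion counts are read against the previous scan but summed over scheduled scans only; if the reader's reference can be an unscheduled scan, lesions drop out of cumulative T2, T2 lesion-free status and CUAL

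*SAP*

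**What the plan says.** SAP 5.3.3.2 fixes how a T2 count is read: "As the number of new or enlarging lesions is always relative to the previous assessment". The same section then introduces the cumulative variables with the restriction "Only scheduled scans are considered, however premature EOT scans are included". The cumulative T2 count is "derived as the sum of the number of new or enlarging T2 lesions at each scheduled scan during the Analysis Period", and absence of new or enlarging T2 lesions over the analysis period is the case where that sum is zero. In 5.3.3.3 the T2 part of cumulative CUAL is "derived as the sum of all new or enlarging T2 lesions at each scheduled scan* within the Analysis Period".

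The offset for the CUAL model (SAP 5.3.4.3) is the log of time to the last T2 scan, and 5.3.3.2 derives that time from scheduled scans. SAP 5.1.3 adds: "Planned pregnancy interruptions will not be excluded for efficacy analyses or for study duration".

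On the protocol side, section 3.3.5 has site staff perform both scheduled and unscheduled MRIs and export them, and 3.11.1.1 has the central reader analyze all MRI data. Section 3.12.5.4 lists an MRI at an unscheduled visit 30 days after drug is interrupted for a planned pregnancy. Section 3.12.5.5, whose title begins "Additional unscheduled visit for eligibility assessment for re-initiation of study drug for female subjects", lists another about 30 days before restart. Appendix 1, section D, keeps the visit schedule during pregnancy with "all the scheduled assessments and procedures except MRI, PFTs and without study drug dispensing".

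**The concern.** Take two scheduled scans with an unscheduled one between them. If each scan is read against the one before it, lesions that appear before the unscheduled scan are recorded there and nowhere else. The scheduled-only sum leaves that scan out, and at the next scheduled scan those lesions are no longer new. The numerator loses them while the offset still contains the time in which they arose.

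The bias has one direction: the annual CUAL rate is too low and the proportion free of new T2 lesions too high. For planned pregnancy the interval concerned is largely off study drug, and SAP 5.1.3 says that interval stays in efficacy.

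The Final CSR outputs affected are the CUAL negative binomial model, the CUAL categories, and T2 lesion-free status over AP3. The cumulative Gd+ and T2 models are not being repeated (SAP 5.3.4.1, 5.3.4.2 and 6.2.3), so CUAL is the only lesion count still modelled. The scheduled-only sentence is not stated for the per-window T2 summaries.

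**Working it through.** **1. The SAP's own example.** A Week 72 scan is read against Week 24, with a window boundary at Week 48. The shares are (48 − 24)/(72 − 24) = 0.5 and (72 − 48)/(72 − 24) = 0.5, which reproduces x/2 and x/2.

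**2. Add an unscheduled scan at week u.** Assume uniform accrual and reading against the previous scan. The share of x missing from the scheduled-only sum is (u − 24)/(72 − 24): 25% at Week 36, 50% at Week 48, 75% at Week 60. Summing over all scans, or reading Week 72 against Week 24, restores x.

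**3. One planned-pregnancy interruption.** Inputs from the protocol:
- maximum interruption 81 weeks = 567 days (Appendix 1, section D)
- first MRI at day 30 (3.12.5.4)
- second MRI 30 days before restart: 567 − 30 = day 537 (3.12.5.5)
- scheduled MRI every 48 weeks = 336 days (visits P1, P5, P9 and so on)
- drug is stopped at a scheduled visit, so 0, 12, 24 or 36 weeks after the last scheduled MRI

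Assumptions: a 280-day pregnancy, conception between day 30 and day 257 (delivery by day 537), and scheduled MRI omitted only during pregnancy.

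Uncounted days = A + B. A runs from the last scheduled MRI to day 30, so A = 30 + 7 × (weeks since that MRI). B runs to day 537 from the latest scheduled MRI done after day 30, or from day 30 if none was done.

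| Weeks since last scheduled MRI | A | Scheduled MRI due (day) | Conception day 30: B, total | Conception day 257: B, total |
|---|---|---|---|---|
| 0 | 30 | 336 | 537 − 336 = 201, total 231 | 537 − 30 = 507, total 537 |
| 12 | 114 | 252 | 537 − 30 = 507, total 621 | 537 − 252 = 285, total 399 |
| 24 | 198 | 168, 504 | 537 − 504 = 33, total 231 | 537 − 168 = 369, total 567 |
| 36 | 282 | 84, 420 | 537 − 420 = 117, total 399 | 537 − 84 = 453, total 735 |

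Every conception day in between gives one of the two totals in its row. The range is 231 to 735 days.

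**4. In lesions.** Protocol 1.3.2.3 quotes 1.405 and 3.164 CUAL per year from the Phase 3 study; they serve only for scale. Low end: 231/365.25 × 1.405 = 0.9. High end: 735/365.25 × 3.164 = 6.4.

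**5. Effect on that patient's rate.** At a constant rate the relative bias is uncounted days divided by offset days. With an assumed offset of 8.02 years (the median 20 mg exposure in protocol 1.3.2.4), 8.02 × 365.25 = 2,929 days. The rate is then low by 231/2,929 = 8% to 735/2,929 = 25%.

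**The case against.** The strongest reply is that the loss depends on a reading rule the documents do not show. The SAP speaks of the previous assessment without saying whether unscheduled scans qualify. Its one example runs from a scan to the next scheduled scan, and the reading instructions are in a separate MRI manual. If scheduled scans are read only against scheduled scans, nothing is lost, and adding unscheduled counts would double-count. This stands, and makes the point conditional. It does not remove it: the example has no intervening scan, so it does not decide the question, and the plain wording points towards the previous scan of any kind.

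Several stronger readings are tempting but unsupported:
- **The whole stretch between the two pregnancy MRIs, 507 days, is always lost.** MRI is waived only during pregnancy, and a scheduled MRI outside it recovers part of that stretch. Conversely, 507 days leaves out accrual before day 30.
- **Diagnostic MRIs for suspected CNS infection behave the same way.** Protocol Appendix 3 describes them without mentioning a new-T2 read.
- **SAP 5.1.3 is defeated.** Interruption time and data do stay in efficacy; what is at risk is part of the lesion count.
- **Every such lesion is lost.** One that enlarges again, or still enhances at the next scheduled scan, can still be counted.
- **The dose comparison is distorted.** Nothing in the documents shows how unscheduled scans fall across dose groups.

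The consequence is also limited. All objectives are exploratory, p-values were removed, and planned-pregnancy interruptions came in only with Amendment 7 in 2017 and had to be requested by Visit P28.

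**Conclusion.** The point holds in conditional form. As written, the reading rule and the summation rule do not fit together, and no passage carries an unscheduled count forward or has the next scheduled scan re-read against the previous scheduled one. If the reference is the previous scan of any type, new non-enhancing T2 lesions first seen on an unscheduled MRI fall out of cumulative T2, AP3 lesion-free status and CUAL, while the offset is unchanged.

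For one interruption at the 81-week maximum the shortfall is about 230 to 735 days of accrual, or about 0.9 to 6.4 lesions. This rests on uniform accrual, the pregnancy and scan timings assumed above, and CUAL rates from a different study on treatment. Women in an interruption are off study drug and may take glatiramer acetate or interferon beta-1a, so their true rate is unknown. The documents give no number of pregnancy or other unscheduled MRIs, so no trial-level bias can be stated.

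**What to change.** Confirm with the central reader which scan T2New_R is compared with, and state it in SAP 5.3.3.2. Then choose the rule.

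- **Previous scan of any type:** sum T2New_R over all AP3 scans at which T2 was read, or add the unscheduled count to the next scheduled scan. Apply this to cumulative T2, T2 lesion-free status and the T2 part of CUAL. Run the offset to the last T2 scan included. Keep the Gd+ part of CUAL on scheduled scans, or add unscheduled scans only where they are at least 12 weeks from adjacent counted scans, in line with the SAP's double-count footnote.
- **Previous scheduled scan:** say so and keep the scheduled-only sum.

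Under the first option the repair is partial. SAP Table 7 defines T2New_R as without gadolinium enhancement, so a lesion enhancing at an unscheduled scan is recovered only if its Gd+ count is also added.

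The cost is SAP wording and at most one derivation change, with no new data and slightly less comparability with the Interim CSR.
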